Pedometer data: Pedometers will be supplied to all participants at the baseline study visit or if preferred participants can use the step counting app embedded in their smart phone (Visit 1), and participants will be asked to wear the devices or keep their phone on them as often as possible during waking active hours. Data will be downloaded by PN in the participants' homes 10 days after the baseline, and for the 10 day prior to visit 2 and visit 3 -week. We will compare average steps per day over the 10-day period prior to visit 2 and visit 3 relative to baseline steps.

L. Collection of Human Biological Specimens:

Fingerstick and serum A1C: The HbA1c test is a blood test that provides information about a person's average levels of blood glucose over the last 3 months. The DCA Vantage Analyzer HbA1c assay tests for a quantitative determination of HbA1c in human whole blood, and provides immediate test results from a finger prick of blood. If remote visit is completed and CHW can not complete A1C then participant maybe asked to go to Labcorp to A1C measurement

Dip Stick urine test: Dipstick urine test will be completed at screening if indicated with immediate results available to review or if needed can be completed at Labcorp

M: Questionnaires : All questionnaires will be available in REDCAP and completed at time of baseline visit with RC in person or remotely. For visit 2 and 3 Redcap surveys will be sent in advance and can be completed by participants in advance and then reviewed with RC or if not completed in advance completed during visit 2 and 3. Assent for household members will be on top of Redcap survey or read to person if in person or on the phone (Appendix N)

Nutrition questionnaire: Starting the Conversation (STC) is an eight-item, simplified food frequency instrument designed and validated for use in primary care and health-promotion settings. It asks respondents to estimate the number of times they consumed certain types of foods over the past week, including fast food, fruits and vegetables, and sugared beverages. Importantly, it has been used and validated in diverse populations including Latinx individuals.⁶⁶ (appendix G). It will also be used for household members >12 years old.

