We will be checking for completion of the questionnaires after links to participants are sent to them and the PHQ-9 responses will be checked at that time. REDCap will be set up so that the research coordinator (RC) is sent a notification when the questionnaire is completed. The RC will check the PHQ-9's completion within 1 hour after being notified if during business hours and within 1 hour of the next business day on the day it has been completed in REDCap. We will minimize likelihood of results occurring outside of business hours by sending surveys in the morning and avoid sending them on Friday as much as able based on participant timeline. Our plan will be put into action if any questions are answered in a manner concerning to our study personnel who will be trained for our action plan and what to watch for within an hour of seeing the answers to the questions.

If the subject endorses suicidal ideation by answering the question yes on the PHQ-9 questionnaire our plan is to:

- Call the participant immediately after review and discuss the participant's answer,
- Provide the participant the number for the local suicide hotline,
- Call the PI if the participant endorses the intent to hurt themselves.
- The PI of the study will be notified immediately and will make the decision to call 911.

The research coordinator (with at least a BS or BA degree) of the study will be trained by the PI who is a licensed MD in all aspects of this questionnaire. The PI be be taking responsibility for this plan of action

Q. Benefits:

Participants may receive some benefit for glucose control for diabetes with RT-CGM and education sessions which may or may not translate to improved long term outcomes complications from diabetes and sugar control. Control patients will likely receive no benefit from blinded CGM but have benefit from educational sessions. This research may benefit society by enhancing our understanding of medical devices use in patients not on prandial insulin especially coupled to education and thus help establish new procedures and practices that are associated with diabetes care

R. Conflicts Of Interest:

[name] is on an advisory board for Novo Nordisk about diabetes medications which was determined not to be a related COI by the University after review.

[name] has also been on an advisory board for DEXCom but review by university determined it did not meet the criteria for significant financial COI.

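### A PHQ-9 completed out of hours waits for next-business-day review with no crisis-line number shown before then, and the plan has no step for a participant who cannot be reached

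*Combined protocol and SAP*

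**What the plan says.** Section P of the combined protocol and SAP, under Plan for PHQ-9 Endorsement of Suicidality, says completion is checked "after links to participants are sent to them and the PHQ-9 responses will be checked at that time". REDCap notifies the research coordinator when a questionnaire is finished. The check is due within an hour "if during business hours and within 1 hour of the next business day on the day it has been completed in REDCap". The plan tries to limit out-of-hours results by "sending surveys in the morning and avoid sending them on Friday as much as able based on participant timeline".

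If suicidal ideation is endorsed on the form, four bulleted steps follow:

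- The first is a telephone contact: "Call the participant immediately after review", to talk through the response.
- The second supplies crisis-line details, which the coordinator passes on.
- The third depends on stated intent: "Call the PI if the participant endorses the intent to hurt themselves".
- The fourth, which has no condition of its own, reads: "The PI of the study will be notified immediately and will make the decision to call 911".

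Section M (Questionnaires) has baseline questionnaires completed at the visit with the coordinator. Later ones differ: "For visit 2 and 3 Redcap surveys will be sent in advance and can be completed by participants in advance and then reviewed with RC".

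**The concern.** The plan foresees out-of-hours completion but controls only when a link is sent, not when it is opened. Someone who endorses suicidal ideation at night or at a weekend would, on the visible text, receive no crisis-line number until staff are back and have read the form. If the call then goes unanswered, no listed step says what the coordinator should do next.

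Endorsement is likely to be uncommon, because section F excludes serious mental illness. It is not ruled out, because people with adequately treated depression remain eligible. This is a participant-safety point. It has no bearing on the endpoints, power or analysis.

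**Working it through.** The plan states no figure to reproduce. The check is a reading of the text plus clock arithmetic.

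**1. Can a PHQ-9 be completed out of hours?** Section M allows visit 2 and 3 surveys to be filled in ahead of the visit. That the PHQ-9 is among them is inferred: section K lists wellness questionnaires at baseline and visits 2 and 3, section P describes links being sent, and the measurement table (Appendix B) is not in the text. Baseline questionnaires are completed with the coordinator, so the links fit visits 2 and 3. The later review with the coordinator is not written as a suicidality step.

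**2. How long until review is due?** The documents do not define business hours. Assume Monday to Friday, opening at 08:00 to 09:00 and closing at 16:00 to 18:00. For a survey completed just after closing:

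wait = (hours from closing to next opening) + 1 h + 24 h × (non-working days in between)

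| Case | Shortest (close 18:00, open 08:00) | Longest (close 16:00, open 09:00) |
|---|---|---|
| Overnight | 14 + 1 = 15 h | 17 + 1 = 18 h |
| Weekend (2 days) | 15 + 48 = 63 h | 18 + 48 = 66 h |
| Three-day weekend | 15 + 72 = 87 h | 18 + 72 = 90 h |

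Hours of 09:00 to 17:00 give 16 + 1 = 17 h, 17 + 48 = 65 h and 17 + 72 = 89 h, inside these ranges. These are the longest waits of each kind. A survey completed later in the evening or weekend waits less, and one completed in business hours or at the visit does not face this wait.

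**3. Is a crisis-line number given earlier?** The only mention in section P is the second step, after the step that follows review. The visible text describes no automatic message in the survey.

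**4. What if the call is not answered?** The plan is triggered by ideation on the form. The third step depends on intent, and the natural place to establish intent is the call. The fourth step says the PI is notified at once, with no condition of its own. There are two readings:

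- The fourth step follows from the third. An unanswered call then establishes no intent, and the PI is not brought in.
- The fourth step applies to every endorsement. The PI is then told whether or not the call is answered, but the condition in the third step does little work.

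The text does not settle which is meant. On either reading, no step is written for a participant who is not reached.

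**5. Does the protocol handle non-response elsewhere?** Yes. In section G, a missed class leads to up to 2 telephone calls, and more than 2 missed sessions without response gives the patient navigator the option of a second home visit. Section H (Baseline Visit) has an emergency contact collected. Section P uses none of these.

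**The case against.** Next-business-day review is a disclosed choice with safeguards around it: automatic notification, a one-hour target, morning sends, Fridays avoided where possible, a trained coordinator, and a PI who takes responsibility for the plan. Round-the-clock cover might be out of proportion for an event likely to be uncommon. That stands, and this point does not ask for such cover. The mitigation is nonetheless best effort.

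Two stronger readings are tempting, and the documents do not support them:

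- A reader might infer that PI notification depends on the call being answered. The fourth step has no condition, and its verb differs from the third (the PI is notified, rather than called), so a two-tier scheme is possible. The link to the decision about 911 favours the narrower reading but does not prove it. The wording is ambiguous, which is less than a demonstrated failure to notify.
- A reader might infer that participants can get a hotline number only after review and an answered call. The steps are unnumbered bullets, and the number could be sent by text or email, which staff already use for reminders. The PHQ-9 form (Appendix P) and the consent form are not in the text, and either could carry a number. What can be said is that the visible plan shows no earlier provision.

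The objection does not remove the deferred review, the absence of a visible automatic message, or the absence of a step for an unreached participant.

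**Conclusion.** The point holds as a participant-safety gap that is cheap to narrow. Review of an out-of-hours PHQ-9 is deferred to the next business day: about 15-18 h overnight and 63-66 h over a weekend at the longest, or 87-90 h over a three-day weekend. The visible plan shows no crisis-line number before that review. It has no step for a participant who cannot be reached, and leaves unclear whether the PI is told in that case.

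This rests on the assumed business hours, the natural reading of a garbled sentence, and the inference that the PHQ-9 is given at visits 2 and 3.

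A reader might multiply 2 visits by the maximum enrolment of 120 and call 240 surveys exposed. That is a ceiling on surveys issued at those visits. It would treat every one as completed in advance and out of hours, which the documents do not say. They give no endorsement rate either, so the number of participants affected cannot be estimated.

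**What to change.** 1. Show crisis-line information in English and Spanish to every respondent on the REDCap completion page. Both languages are needed because section D expects a roughly even split. This does not shorten the review delay, but the number no longer has to wait for it. If Appendix P or the consent form already carries a number, the message only reinforces it.

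2. Add one step: if a participant with a positive self-harm answer is not reached on the day of review, for example after 2 calls, the PI is notified that day and decides on further action, including whether to use the emergency contact on file. The number of calls is a matter of preference; 2 matches the missed-class rule in section G and has no separate safety rationale.

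The cost is one two-language survey message and one added step. The downside is occasional extra PI notifications for people who simply missed a call. Contacting a third party also carries a confidentiality cost, since section S limits personal information to the PI and research staff; that decision is left to the PI. Design, sample size and analysis are unchanged.
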